11.5.3 Procedures for Discontinuation or Withdrawal of a patient

There are no special procedures of discontinuation of patients. The investigator may terminate a patient's study participation at any time during the study when the patient meets the study termination criteria described above in Section 11.5.1. In addition, patient/legal representative may discontinue participation in the study without giving a reason at any time during the study.

In all cases, the reason for withdrawal must be recorded in the eCRF and in the patient's medical records. The patients who prematurely withdrew from the study are not replaced with new ones, and their data will be included into the final analysis. In case if investigator loses contact with the patient during the study observation, the investigator may contact with the patient directly or through the other health care professionals who observe this patient in routine practice. In that case part of eCRF "End of observation" can be filled in basing on data received via e-mails/calls.

12 Data collection

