15.4 Determination of Sample Size

The primary objective of this study is to obtain the accurate and comprehensive information regarding the treatment regimens used in patients with moderate to severe UC and CD flare within routine clinical practice in Russia, Belarus and Kazakhstan. For this purpose, sample size should be large enough to contain essential number of patients with different therapy options.

One of the key secondary objectives is to assess the percentage of Ulcerative Colitis (UC) and Crohn's Disease (CD) patients with at least one episode of failure of non-biological therapy with immunosuppressive agents or biological therapy registered within 12 months from the beginning of moderate to severe IBD flare. Based on literature data, up to 20-40% of IBD patients

experience failure of TNF antagonist therapy initially, and in 10-20% of patients per year loss of response is observed.

Assuming the percent of patients receiving biological therapy in the study population is 40%, about 40% proportion of CD patients [5, 6] and that 40-50% of the patients on biological therapy will have at least one episode of treatment failure during 12 months, enrolment of 2000 patients totally will be sufficient to estimate the proportion of patients on biological therapy with treatment failure during the 12 months of observation with acceptable precision in both UC and CD subgroups ($\pm 5.8\%$ for the smaller subgroup of CD patients and the assumed failure rate of 50%). The table below shows 95% confidence intervals for the estimated proportions of 40%, 50% and different sample size values. For other, more prevalent subgroups (CD patients on non-biological therapy, UC patients on each type of therapy) the proposed sample size will also allow to estimate proportion of patients with treatment failure with same or higher precision.

The total number of patients to be enrolled	The number of CD patients on biotherapy*	The number of CD patients in the analysis assuming 10% drop-out	Assumed failure rate of biotherapy**	
			40%	50%
2000	320	288	34.3-45.7%	44.2-55.8%
2500	400	360	34.9-45.1%	44.8-55.2%
3000	480	432	35.4-44.6%	45.3-54.7%
3500	560	504	35.7-44.3%	45.6-54.4%
4000	640	576	36.0-44.0%	45.9-54.1%
4500	720	648	36.2-43.8%	46.2-53.8%
5000	800	720	36.4-43.6%	46.3-53.7%

* Assuming the percent of patients receiving biotherapy is 40% among the study population. The precision (95% CI) is shown for the smaller subgroup of CD patients (approximately 40%).

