** 95% confidence intervals are shown.

16 Reports

A Non-Interventional Study Report based on the results obtained will be prepared and submitted to the Sponsor for distribution. The Final Non-Interventional Study Report should be available within one year (12 months) from the date of the last data point collection, and the participating sites should be informed about the results when the report is finalised. Final Non-interventional Study Report should be provided to the IEC/RA (if applicable).

17 Publications

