#### 8.1.3 Assessment of secondary and exploratory endpoints

**Each original treatment combination** (defined as the treatment combination that was used by the patient at the very start of retrospective observation period, i.e. first recorded treatment combination in the study) will be tabulated by the below listed parameters using the generic table format below (see example tables: Table 10, Table 11, Table 12 and Table 6):

- Demographic data;
- Disease activity at Visits 1, 2, 3 (Mayo, Harvey-Bradshaw indices);
- Disease status assessed by investigator at Visits 1, 2, 3;
- Frequency (percentage) of clinical, endoscopic and histologic remission at Visits 1, 2, 3 and retrospective period of observation;
- Extent of lesion at Visits 1, 2, 3;
- Systemic (extraintestinal) manifestations at Visits 1, 2, 3;
- Total number, duration and severity of disease exacerbations by Visit 1, 2 and 3;
- Total number, type and duration of disease complications by Visit 1, 2 and 3;
- Laboratory and instrumental assessments at Visits 1, 2, 3;
- Percentage of patient with surgical treatment by Visits 1, 2, 3 grouped by:
  - Indication;
  - Surgery type;
  - Presence of complications.
- Number of surgeries by Visits 1, 2, 3;

Protocol ID	MACS-2017-102279	STATISTICAL ANALYSIS PLAN	Page 25 of 41	
IP	N/A		Date	30.12.2021
ID	MACS-2017-102279_SAP		Version	v1.2 final

- Percentage of patients with at least one episode of failure or biological or/and non-biological therapy (e.g., dose escalation of biologics, switching to another therapy, IBD-related surgery, medication augmentation) by Visits 1, 2 and 3;
- Separately for patients who achieved / not achieved T2T treatment goals (based on the clinical assessment of IBD) by Visits 1, 2 and 3:
  - Presence of therapeutic de-escalation;
  - Presence of therapeutic escalation;
  - Continuation of therapy without any changes.
- Healthcare resources utilization:
  - Hospitalizations due to complications;
  - IBD-related surgeries;
  - Percentage of patients that used healthcare resources;
- Only for biological therapy - percentage (by Visits 1, 2, 3) of patients with:
  - Positive test results for TB before the start of biological therapy;
  - Active TB before the start of biological therapy;
- Percentage of patients by Visits 1, 2, 3 with:
  - Reactivation of TB;
  - New occurrence of TB.

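### The 12-month failure percentage has no rule for patients lost before month 12, and the sample size removes drop-outs whom the analysis keeps

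*Protocol*

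**What the plan says.** **Sample size.** Protocol 15.4 starts from these inputs: "Assuming the percent of patients receiving biological therapy in the study population is 40%, about 40% proportion of CD patients", and "40-50% of the patients on biological therapy will have at least one episode of treatment failure during 12 months". It concludes that "enrolment of 2000 patients totally will be sufficient to estimate the proportion of patients on biological therapy with treatment failure"; the window is the year of observation, and the precision is judged adequate for UC and CD alike. The stated precision, ±5.8 points at 50% failure, belongs to the 288 patients in the column headed "The number of CD patients in the analysis assuming 10% drop-out". SAP 8.2 repeats the table but argues from 3000 patients.

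**Who is analysed.** Protocol 11.5.3 says: "The patients who prematurely withdrew from the study are not replaced with new ones, and their data will be included into the final analysis". SAP 5.4.2 repeats this. Protocol 15.1 rules out exclusion for lack of data. Protocol 15.2.4 answers attrition bias by collecting the last data of early leavers and keeping them in the effectiveness analysis. SAP 8.6, however, allows some patients or a whole centre to be left out because of missing data.

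**How failure is reported.** Protocol 6.2 and SAP 6.1 define failure as ever/never. SAP 8.1.3 tabulates it by visit as "Percentage of patients with at least one episode of failure or biological or/and non-biological therapy". Percentages use the non-missing number (Protocol 15.2.1, SAP 8.1.1), and nothing is imputed (Protocol 15.2.5, SAP 8.4). Kaplan-Meier estimates are planned for time-to-event data (Protocol 15.2.2, SAP 8.1.1), but neither document lists failure as such an outcome.

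**The concern.** A 12-month risk cannot be read directly from a count when some patients are observed for less than 12 months. The plan keeps those patients but gives no rule for scoring them and no estimator that uses their partial follow-up. The result then depends on how the failure flag is programmed, and the confidence interval does not show that choice.

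Failure is a secondary outcome, but it is the one that justifies the sample size. It is also presented by therapy group, so unequal loss between biologic and non-biologic patients could produce a difference that is not real.

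The precision statement is affected too. It refers to 288 patients, while the analysis text points to 320.

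**Working it through.** **Step 1. Reproduce the plan's figures.** The table's footnote says "95% confidence intervals are shown".

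- CD patients on biologics: 2000 × 0.40 × 0.40 = 320. After 10% drop-out: 320 × 0.90 = 288.
- Half-width at 40%: 1.96 × √(0.4 × 0.6 / 288) = 5.66 points, giving 34.3–45.7%.
- Half-width at 50%: 1.96 × √(0.5 × 0.5 / 288) = 5.77 points, giving 44.2–55.8%.

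All seven rows reproduce to one decimal with this normal approximation. Clopper-Pearson, the method planned for binary data, gives 34.2–45.8% and 44.1–55.9% at n = 288. With 320 patients the half-widths are 5.37 and 5.48 points. The table has no arithmetic error.

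**Step 2. Percentage under each way of scoring early losses.** The 10% loss and the true rates p = 40% and 50% come from Protocol 15.4. Constant hazard, equal risk in drop-outs and the timing of loss are assumptions.

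Let q be the probability that a drop-out's failure is seen before loss, and h = −ln(1 − p).

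- Loss spread evenly over the year: q = 1 − p/h. For p = 0.5, h = 0.693 and q = 0.279. For p = 0.4, h = 0.511 and q = 0.217.
- Loss at 6 months: q = 1 − √(1 − p), which is 0.293 and 0.225.
- Loss at baseline: q = 0.

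If unrecorded means no failure, the percentage is 0.9p + 0.1q. If patients lost without a failure are set to missing but earlier failures are kept, it is (0.9p + 0.1q) / (0.9 + 0.1q).

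| Handling and timing of loss | True 40% | True 50% |
|---|---|---|
| Non-failure, spread over the year | 38.2% | 47.8% |
| Non-failure, all at 6 months | 38.3% | 47.9% |
| Non-failure, all at baseline | 36.0% | 45.0% |
| Missing, earlier failures kept, spread over the year | 41.4% | 51.5% |
| Completers only, loss unrelated to failure | 40.0% | 50.0% |
| Kaplan-Meier, independent censoring | 40.0% | 50.0% |

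Worked case for p = 0.5 with even loss: 0.45 + 0.0279 = 0.478, and 0.478 / 0.928 = 0.515.

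**Step 3. Effect on the interval.** With n = 320, a 95% interval centred on 47.8% would cover a true 50% about 88% of the time. Centred on 45.0%, it would do so about 56% of the time.

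**Step 4. Sensitivity to the assumptions (illustrative values).**

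- Drop-outs at higher risk: if 80% of them would fail and all are lost at baseline, the true rate is 0.9 × 0.5 + 0.1 × 0.8 = 53%. The non-failure rule still reads 45.0%, which is 8 points low.
- Unequal loss: with 5% lost in one therapy group, 15% in the other and 50% true failure in both, the non-failure rule gives a false difference of 0.10 × (0.5 − 0.279) = 2.2 points for even loss, and 0.10 × 0.5 = 5.0 points for loss at baseline.
- Bounds: with even loss at p = 0.5, the share lost without a recorded failure is 0.1 × (1 − 0.279) = 7.2%. Scoring them all as non-failures or all as failures gives 47.8% to 55.0%.

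**The case against.** The strongest objection is that no section says an early-lost patient counts as a non-failure. Percentages use non-missing observations, nothing is imputed, failure is tabulated by visit, and SAP 8.6 allows exclusions. A patient without V3 data could simply be absent from the V3 denominator. In that case 288 is about the right number, and it is conservative against 320. A reader might infer that the plan certainly biases failure downward. The documents do not support that: under the missing rule the bias is upward, and with completers only it is zero if loss is unrelated to failure.

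That part stands. Three things still make the non-failure reading the likely default. Failure is built from recorded events (dose escalation, switching, surgery, augmentation), so a patient lost at month 2 has a flag that reads no rather than a blank field. Protocol 15.2.4 keeps early leavers on their last data. The SAP abbreviation list defines n as patients with an event and N as all patients in the group, which fits n/N without proving it.

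A second objection concerns the time origin. Protocol 15.4 counts failure both from the start of the flare and over the 12 months of observation. The flare may lie up to two years before enrolment (Protocol 11.1), and loss after V1 would not truncate a window that closed before then. This also stands, and the fix has to settle it.

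A third is that Kaplan-Meier relies on independent censoring, which is doubtful when adverse events or lack of efficacy can lead to withdrawal (Protocol 11.5.1). That calls for bounds alongside the estimate. It does not make the raw percentage safer.

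**Conclusion.** The concern holds as a gap in definition with a conditional bias. The sample size removes drop-outs whom the analysis keeps, failure status under incomplete follow-up is undefined, and no method that handles censoring is assigned to failure.

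At the plan's own 10% loss spread over the year, with constant hazard and equal risk in drop-outs, the two ways of forming the percentage while keeping early leavers differ by 51.5 − 47.8 = 3.7 points for a true 50%. Each is off by about 2 points or less. A reader might take the bias to be as large as the stated ±5.8. Under equal risk that is approached only if every loss occurs at baseline (5.0 points at 50%, 4.0 at 40%). The bias exceeds it if drop-outs fail more often than others, and the documents give no figure for that.

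The study is descriptive and the table's arithmetic is correct, so this does not undermine the design. It should be corrected because the bias does not shrink with sample size.

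**What to change.** 1. Make the main failure estimate the 12-month cumulative incidence from V1, which matches the observation period in Protocol 15.4, and reconcile this with the flare-based wording in the same section.
2. Censor at the date of last contact and treat death as a competing event. With no deaths this equals one minus Kaplan-Meier. Use the log-log 95% CI already named in SAP 8.1.1.
3. Keep the raw percentage as a secondary row. State its denominator and how patients with under 12 months of follow-up and no recorded failure are scored.
4. Add best-case and worst-case bounds for lost patients, because withdrawal for adverse events or lack of efficacy may make censoring informative.
5. State in Protocol 15.4 whether precision refers to 320 or 288, and align SAP 8.2.

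**Cost.** Small. Date of last contact is recorded for every patient who passed the baseline visit (Protocol 12.5; also SAP 5.4), drug start and end dates are collected (Protocol 12.6.1), and the interval method is already in the SAP. The downside is dating some components of failure. The steroid fields list a maximum daily dose without its date, and surgery dates are not listed explicitly. These may have to be taken from eCRF records or assigned to the interval between visits.

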17.1 Publication and Disclosure

During the study, only the Sponsor may make study information available to other study investigators or to regulatory agencies, except as required by law or regulation. Except as otherwise allowable in the study site agreement, any public disclosure (including publicly accessible websites) related to the protocol or study results, other than study recruitment materials, is the sole responsibility of the Sponsor.

The Sponsor may publish any data and information from the study (including data and information generated by investigators) without the consent of investigators. Manuscript authorship for any peer-reviewed publication will appropriately reflect contributions to the production and review of the document. All publications and presentations must be prepared in accordance with this section and the study contracts. In the event of any discrepancy between the protocol and the study contracts, the study contracts will prevail.

The Sponsor aims to have the results of this study published and acknowledges the right of the participating sites to publish results from this study. The Sponsor has the right to use the data and results for regulatory purposes and for internal presentation within the company, to affiliates and partners

Appendix 1. Montreal classification of extent of ulcerative colitis

Extent	Anatomy
E1	Ulcerative proctitis
E2	Left sided UC (distal UC)
E3	Extensive UC (pancolitis)

Appendix 2. Montreal classification for Crohn's disease

Age at diagnosis	A1 below 16 y
	A2 between 17 and 40 y
	A3 above 40 y
Location	L1 ileal
	L2 colonic
	L3 ileocolonic
	L4 isolated upper disease*
Behaviour	B1 non-stricturing, non-penetrating
	B2 stricturing
	B3 penetrating
	p perianal disease modifier†

*L4 is a modifier that can be added to L1–L3 when concomitant upper gastrointestinal disease is present.

† “p” is added to B1–B3 when concomitant perianal disease is present.

Appendix 3. Mayo score

The full Mayo Score evaluates ulcerative colitis stage, based on four parameters: stool frequency, rectal bleeding, endoscopic evaluation and Physician's global assessment (1,2). Each parameter of the score ranges from zero (normal or inactive disease) to 3 (severe activity). The following table indicates, for each parameter, the input values with their respective scores.

Parameter	Clinical evaluation (single choice)	Score
1. Stool frequency (per day)	
 normal number of stools 1-2 more than normal 3-4 more than normal ≥ 5 more than normal 	0 1 2 3
2. Rectal bleeding (indicate the most severe bleeding of the day)	
 none streaks of blood with stool in less than half of the cases obvious blood with stools in most cases blood alone passes 	0 1 2 3
3. Endoscopic findings	
 normal mucosa or inactive disease mild activity (erythema, decreased vascular pattern, mild friability) moderate activity (marked erythema, lack of vascular pattern, friability, erosions) severe activity (spontaneous bleeding, large ulcerations) 	0 1 2 3
4. Physician's global assessment	
 normal mild disease moderate disease severe disease 	0 1 2 3

Calculation formula: sum of the scores of the four parameters.

Score	Decoding
0 - 2	Remission (provided that no subscore for each single parameter is greater than 1)
3 - 5	mild activity
6 - 10	moderate activity
> 10	severe activity

Partial Mayo Score uses the three non-invasive components of the full Mayo Score (stool frequency, rectal bleeding and Physician's global assessment). This excludes the score for the endoscopic findings, therefore the maximum score is reduced from 12 to 9 points (1,2). This simplified index maintains a good relationship with the full Mayo Score in identifying clinical response as perceived by patients (3).

Score	Decoding
<2	remission
2 - 4	mild activity
5 - 7	moderate activity
> 7	severe activity

Appendix 4. Harvey-Bradshaw index

Parameter	Input and score
1. Patient well-being (previous day)	0 = very well 1 = slightly below par 2 = poor 3 = very poor 4 = terrible
2. Abdominal pain (previous day)	0 = none 1 = mild 2 = moderate 3 = severe
3. Number of liquid or soft stools (previous day)	blank field possibility to insert an integer, from 1 to 25
4. Abdominal mass	0 = none 1 = dubious 2 = definite 3 = definite and tender
5. Complications	No (0 points) Yes (drop-down menu with multiple selection; each selected complication is counted with 1 point) 
• arthralgia• uveitis• erythema nodosum• aphthous ulcer• pyoderma gangrenosum• anal fissures• appearance of a new fistula• abscess

Calculation formula: sum of the scores of all 5 parameters.

Score	Decoding
<5	remission
5 - 7	mild activity
8 - 16	moderate activity
> 16	severe activity

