4.3 IBD activity assessment

Validated Mayo score evaluates ulcerative colitis stage, based on four parameters (full Mayo score): stool frequency, rectal bleeding, endoscopic evaluation and physician's global assessment (see **Appendix 3**). Each parameter of the score ranges from zero (normal or inactive disease) to 3 (severe activity). The partial Mayo score uses the three non-invasive components of the full Mayo Score (stool frequency, rectal bleeding and Physician's global assessment). This excludes the score for the endoscopic findings; therefore, the maximum score is reduced from 12 to 9 points. The full or partial Mayo score (in accordance with routine clinical practice) will be evaluated at each study visit.

Harvey-Bradshaw index (HBI) is used in the assessment of Crohn's disease activity (see **Appendix 4**). It is a validated clinical index for CD, including the 5 categories of: general well-being, abdominal pain, number of liquid stools, abdominal mass and complications. The score ranges from 0 to 25 with higher scores indicating higher disease activity. The scores were classified as follows: less than 5 is remission, 5 to 7 is mild, 8 to 16 is moderate, and greater than 16 is severe. HBI will be evaluated at each study visit.

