4.4 Treat to target approach in IBD treatment

"Treat to target" approach - evidence- and consensus-based recommendations for selecting the goals for treat-to-target strategies in patients with IBD. A "Treat to target" approach for UC includes clinical remission (defined as resolution of rectal bleeding and diarrhea/ altered bowel habit) and endoscopic remission (defined as Mayo endoscopic subscore of 0–1). Biomarker remission (normal C-reactive protein (CRP) and calprotectin) is considered as an adjunctive target. Histological remission is considered as an adjunctive goal [17, 21].

Clinical remission for CD is defined as resolution of abdominal pain and diarrhea/ altered bowel habit. Endoscopic remission for CD is defined as resolution of ulceration at ileocolonoscopy or resolution of findings of inflammation on cross-sectional imaging in patients who cannot be adequately assessed with ileocolonoscopy. Biomarker remission (normal C-reactive protein (CRP) and faecal calprotectin) is considered as an adjunctive target [14, 21].

Treat to target approach achievement will be evaluated at observational (Month 6) and final (Month 12) visits.

5 Introduction

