12.4 Data collected at the Observational visit (V2) and Final Visit (V3)

Data to be collected directly on Observational visit (V2) and Final visit (V3):

- Date of visit (day, month, year)
- Type of visit: visit to physician office or distant contact
- Physical examination: weight (kg), body mass index calculation;
- IBD assessment at the time of the visit:
 - Disease extent according to the following Montreal Classification categories;
- Disease activity data at the visit will consist of specified signs and symptoms depending on the disease type:
 - CD: abdominal pain severity, number of liquid stools per day, presence of an abdominal mass, endoscopic findings (if done), documented presence of CD complications, and Harvey Bradshaw Index or other documented disease activity scales (if applicable).
 - UC: frequency of stools/day, rectal bleeding, endoscopic findings (if done), physician global assessment of disease severity, and Mayo scores or other documented disease activity scales (if applicable).
- IBD status (with current/last available data by the date of the visit):

- IBD status as judged by investigator (remission, incomplete remission, flare, others), nature of remission at the time of examination;
- IBD flare(s);
- Systemic (extra intestinal) IBD manifestations;
- IBD complications;
- Vaccination in accordance with IBD treatment guidelines.
- Laboratory and instrumental evaluation of IBD (if done within routine practice) - for details please section 12.8;
- IBD treatment;
- IBD surgical treatment;
- Healthcare resources utilization;
- Concomitant treatment
- Adverse events and adverse drug reactions (seriousness, severity, causality, start and stop dates, action, frequency, outcomes):
 - adverse drug reactions on IBD treatments,
 - adverse events on Entivyo® (Vedolizumab) treatment,
 - serious adverse events on IBD treatments (including Entivyo® (Vedolizumab) treatment).

All adverse events and adverse drug reactions must be documented on the Adverse Report Form which is appended to the Case Report Form.

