### 8.4 Handling of missing or incorrect data

Assigned data manager and statistician will continuously identify missing, questionable or non-interpretable data in the study database, and queries will be generated to study sites to address this.

All missing, questionable or non-interpretable data that were not clarified through query generation process will be treated as missing and not included in the final statistical database for interim and final analyses. Listing of such data will be provided as an attachment to the statistical analysis report, if applicable.

Protocol ID	MACS-2017-102279	STATISTICAL ANALYSIS PLAN	Page 29 of 41	
IP	N/A		Date	30.12.2021
ID	MACS-2017-102279_SAP		Version	v1.2 final

Missing data will not be restored. No procedures for missing data pattern assessment and/or imputation are planned.

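### The Harvey-Bradshaw stool item has no valid entry for zero stools, and its printed items do not give the score range stated in the protocol

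*Protocol*

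**What the plan says.** Protocol Appendix 4 prints the five HBI items. Well-being (0–4), abdominal pain (0–3), abdominal mass (0–3) and complications all have an explicit zero. The stool item does not: its entry is "blank field possibility to insert an integer, from 1 to 25". For complications, "each selected complication is counted with 1 point", and eight are listed. The total is a plain sum: "Calculation formula: sum of the scores of all 5 parameters".

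Protocol section 4.3 describes the same index differently: "The score ranges from 0 to 25 with higher scores indicating higher disease activity". Its classes are "less than 5 is remission, 5 to 7 is mild, 8 to 16 is moderate, and greater than 16 is severe". Section 4.3 counts liquid stools, and so do the data lists in 12.3 and 12.4 (in 12.4, "CD: abdominal pain severity, number of liquid stools per day, presence of an abdominal mass"). Appendix 4 counts liquid or soft stools on the previous day.

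The T2T definition in section 4.4 does not use the HBI: "Clinical remission for CD is defined as resolution of abdominal pain and diarrhea/ altered bowel habit".

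Under SAP 8.4, missing or questionable values that remain unresolved after queries "will be treated as missing and not included in the final statistical database for interim and final analyses", and nothing is imputed. Percentages are based on non-missing observations (Protocol 15.2.1, SAP 8.1.1).

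**The concern.** Having no liquid stools is an ordinary finding in a CD patient who is doing well, and the printed form has no number for it. A site can enter 1, leave the field empty, or enter a 0 that the form does not list. The documents do not say which is intended, or whether empty means zero or not assessed. Each choice gives a different HBI.

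The HBI is reported in its own right in several places:

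- It is analysed by its scale definitions (Protocol section 2, statistical methods).
- At Visit 1 it breaks down the treatment patterns (SAP 8.1.2).
- It is tabulated at Visits 1, 2 and 3 (SAP 8.1.3).
- It defines the under-5, 5–16 and over-16 subgroups of first-line biological therapy (SAP 7.4).
- It is compared with investigator-judged status (SAP 8.7, 2019 analysis, item 10).

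If zero-stool patients are scored too high or dropped, these results are off at the low end of the scale, where remission is decided.

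**Working it through.** **1. Reproduce the stated range.** The inputs are the Appendix 4 items.

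- Minimum as printed: 0 + 0 + 1 + 0 + 0 = 1.
- Maximum: 4 + 3 + 25 + 3 + 8 = 43.
- If 0 is allowed for stools, or an empty field counts as 0, the minimum is 0 and the maximum stays 43.

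The 0–25 in section 4.3 is not reproduced under any of these readings. The lower end agrees only once zero is permitted. The upper end never agrees.

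**2. Zero stools entered as 1.** Let s be the sum of the other four items. The true HBI is s and the recorded HBI is s + 1.

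- s = 0, 1, 2, 3 gives 1, 2, 3, 4: still remission (<5).
- s = 4 gives 5: remission becomes mild.

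So remission status changes only at s = 4. By the same arithmetic, s = 7 moves mild to moderate and s = 16 moves moderate to severe. Let R be the true HBI remission rate and f the share of remitters with zero stools and s = 4. The recorded rate is R(1 − f). The documents give neither value. Assuming R = 50% and f from 0 to 10%, the recorded rate is 50.0% to 45.0%.

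**3. Field left blank and still missing after queries.** The five-item sum cannot be formed and the patient leaves the non-missing denominator. Let q be the share of remitters, and q0 the share of non-remitters, with zero stools:

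recorded rate = R(1 − q) / [R(1 − q) + (1 − R)(1 − q0)]

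R, q and q0 are all assumptions. With q0 = 0:

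| True rate R | q = 20% | q = 50% | q = 80% |
|---|---|---|---|
| 30% | 25.5% | 17.6% | 7.9% |
| 50% | 44.4% | 33.3% | 16.7% |
| 70% | 65.1% | 53.8% | 31.8% |

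For example, with R = 50% and q = 20%: 0.40 / (0.40 + 0.50) = 44.4%.

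The result depends on q0. With R = 50% and q0 = 5%, the middle row becomes 45.7%, 34.5% and 17.4%. Out of 100 patients, 50 of them remitters, blanks for 20 remitters and 10 non-remitters give 30/70 = 42.9%; blanks for the 20 remitters alone give 30/80 = 37.5%. If q = q0, there is no bias.

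**4. Blank counted as 0.** Patients who were assessed are scored correctly. But Visits 2 and 3 may be distant contacts (Protocol 12.4), and a stool item that was never assessed then looks the same as no stools and lowers the HBI.

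**The case against.** The strongest reply is that the printed range may be only a loose description of a free-entry box. An empty field may have been meant to add nothing, which fits the lower limit of 0 in section 4.3. The eCRF screen and its edit checks are not in the documents, so it may have accepted 0. A blank would normally be queried (Protocol 14.1.4 and 14.3.3, SAP 8.4) before being treated as missing. The 25-versus-43 maximum moves nobody between classes, because the severe class has no upper limit. The analysis is descriptive. All of this stands as a limit on the consequences. It does not supply the missing rule, and it does not reconcile the appendix with section 4.3.

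A reader might also infer three stronger things that the documents do not support.

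- *That the CD remission endpoint is biased.* The secondary outcome follows the T2T definitions, which for CD are symptom-based (Protocol 4.4 and 6.2). SAP 8.1.3 judges T2T failure from investigator feedback and objective methods, and SAP 8.7 names the HBI among objective methods. That is a possible route, but no section derives T2T remission from an HBI below 5 or from this field.
- *That no CD patient can be recorded with zero stools.* Sections 12.3 and 12.4 list liquid stools per day alongside the HBI, with no range restriction, so that item may hold a zero.
- *That the error always lowers remission, or affects remitters generally.* Entering 1 changes remission status at a single value of the other items. The blank route lowers the rate only to the extent that zero stools are more common among remitters. Counting blank as 0 can push the score down.

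**Conclusion.** The defect is real as written. The stool item has no valid numeric entry for zero, an empty field has no defined score, the stated range of 0–25 does not match items that sum to 1–43, and the item is worded in two ways.

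The size of the effect on results is unknown, because the documents do not show how zero was entered. The entered-as-1 route is small for remission status. The material risk is blank treated as missing: from a true HBI remission rate of 50%, the recorded rate could be 44% to 17%. That range rests on an assumed 20% to 80% of remitters, and no non-remitters, having zero stools. It is an illustration and not an estimate.

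The exposed results are the HBI summaries by visit, the Visit 1 activity breakdown of treatment patterns, the HBI subgroups (if scored on this form) and the comparison of investigator status with HBI. T2T remission is affected only if resolution of diarrhoea is derived from this field, which the documents do not say.

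**What to change.** In the text:

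- State in Appendix 4 and in the SAP that 0 is a valid stool value and that blank means not assessed.
- Use one wording of the item (liquid, or liquid or soft) in 4.3, 12.3, 12.4 and Appendix 4.
- Correct the range in 4.3 to match the items: 0–43 once 0 is allowed.

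In the data: the SAP is dated 30.12.2021 and data collection was planned to end in Q3–Q4 2021 (Protocol 10.2), so changing the eCRF probably comes too late. Before computing HBI, establish how the eCRF took a zero. Compare HBI stool entries of 1 or blank with the separately recorded number of liquid stools per day, and query disagreements. They should not be overwritten automatically, because a patient with soft but no liquid stools can properly differ on the two items. If the eCRF accepted 0 and kept it distinct from blank, confirming that closes the data question and only the text corrections remain.

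The cost is a small amount of extra data checking, with no extra patients or procedures.
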